9.1 Study Design

9.1.1 Design Overview

This is a prospective, observational, multicenter, 30-month, Phase IV study. Sites in the US who are known to treat patients with MS will be targeted for enrollment. Patients who had decided prior to enrollment to transition from an oral DMD or an infusion DMD to treatment with cladribine tablets under routine clinical care and who meet all eligibility criteria consistent with the approved US Prescribing Information (USPI) will receive an initial treatment course with cladribine tablets in Year 1 and are planned to receive a second course in Year 2, as per the approved USPI. Cladribine tablets are being prescribed as part of patients' standard medical care and commercial product will be used. Patients will not be provided the cladribine tablets free of charge in connection with their participation in the study. It is expected that the investigator considered the mode of action and duration of effect of the previous DMD prior to initiation of cladribine tablets. It is at the investigator's discretion to define this time period, following respective USPI.

Baseline PROs, MRI and treatment adherence data will be collected before the first dose of cladribine tablets is taken. Baseline data on previous MS DMD use and relapses during the previous 2 years (or since MS diagnosis, if diagnosis <24 months) will be collected retrospectively at the Baseline Visit. All treatment decisions are at the discretion of the investigator. Patients will be followed up until the end of the observation period, irrespective if they discontinue cladribine tablets during follow-up.

During the observation period, patients will attend visits as per routine clinical practice, which are expected to happen approximately at the end of Months 2, 6 and 12 during Year 1, and at the end of Months 14, 18, and 24 during (i.e. after the second course of treatment during Year 2), as clinically indicated.

Post-enrollment relapse count data will be collected at Month 12 (end of Year 1) and Month 24 (end of Year 2) only. Treatment adherence data during treatment with cladribine tablets will be collected at the end of Months 1, 2, 13, and 14, while other PROs will be collected at the end of Months 6, 12 and 24¹.

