9.2.4 Frequency of Assessments

Table 1 lists the Schedule of Assessments. Patients are considered enrolled once the informed consent form (ICF) has been signed prior to any data collection for this study. The Baseline Visit is the visit immediately prior to the patient initiating treatment with cladribine tablets. If the sites anticipate a delay between the decision to start cladribine tablets and patient access to cladribine

tablets (i.e. due to delays in cladribine tablets availability or access), the site can perform a Screening Visit first to determine eligibility of the patient and a subsequent Baseline Visit closer to the time the patient starts taking cladribine tablets. Data entered during the Baseline Visit are considered baseline data for the purposes of analysis.

Sites are asked to enter patient follow-up data for up to 24 months after a patient received the initial month dose of cladribine tablets if Year 2 treatment course is not delayed, and up to 30 months after initial dose if Year-2 treatment course is delayed up to 6 months. Visits will be conducted within the context of routine clinical care; thus, the timing of study visits is approximate and not mandated by the study protocol.

It is anticipated that patients enrolled in the study may not immediately start cladribine tablets after the decision to initiate cladribine tablets is made, owing to the need to first discontinue their current oral or infusion DMD (for a time period determined by the investigator) and to potential delays in obtaining cladribine tablets in the clinical setting. The initial PRO only collection (Month 1) is intended to be obtained after the patient has started treatment with cladribine tablets. The timing of Visit 1 (Month 2) and the subsequent visits may need to be adjusted based upon the actual start date of cladribine tablets, which will be recorded by the investigator.

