### **Conversion Factors**

The following conversion factors will be used to convert days into months or years:

*1 month = 30.4375 days, 1 year = 365.25 days.*

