## **14                    Efficacy Analyses**

### **14.1                Primary Endpoint: ARR**

#### **14.1.1            Primary Objective: Analysis of the ARR**

Analysis (Analysis Population)	Derivation	Statistical Analysis Methods	Missing Data Handling
Primary endpoint: ARR over 24 Months			
Primary (FAS)	
ARR over 24 months. The ARR over 24 months of a patient is calculated as the number of relapses of the patient, divided by the number of days on study for that patient and multiplied by 365.25. This variable will be considered to get population estimates.
 
A relapse will be defined as per routine clinical practice, as determined by the Investigator.
 
Time on study (days) = (Date of study completion or date of study discontinuation - date of first dose of cladribine tablets + 1)
	
The population estimate will be based on the average of the ARR values for the patients in the study. The corresponding 95% CI will be reported. The Statistical Analysis System (SAS)® MEANS procedure will be used to compute these quantities. The following descriptive statistics will be reported: mean, SD, min, max, median, first quartile (Q1), and third quartile (Q3).
	
Patients discontinuing early are analyzed according to the number of years of follow-up on treatment and the number of relapses observed up to the time of discontinuation.

Secondary (PP)			

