Sensitivity (FAS)	
Model-based ARR, defined as expectation of relapses divided by time on study.
	
The estimate of the expected ARR at Month 24 will be based on a negative binomial (NB) model for relapse count, with offset equal to the log of years on study and adjustment for categorical number of relapses in the last 2 years, or since MS diagnosis if diagnosis <24 months (<math>\leq 1</math> relapse, <math>>1</math> relapse). NB regression will be computed with the SAS® Generalized Linear Model (GENMOD) procedure, using the dist=NB option in the MODEL statement.
 
*The estimate of the expected ARR at Month 24 will be based on a zero-inflated NB model for relapse count, with the offset equal to the log of years on study and adjustment for categorical number of relapses in the last 2 years, or since MS diagnosis if diagnosis <24 months (<math>\leq 1</math> relapse, <math>>1</math> relapse). NB regression will be computed with the SAS® GENMOD procedure, using the dist=ZINB option in the MODEL statement.
	
Same handling as for the primary analysis.

Analysis (Analysis Population)	Derivation	Statistical Analysis Methods	Missing Data Handling
Sensitivity (FAS)	
ARR over 24 months considering all reported relapse data. For a patient, such ARR is calculated as the total number of reported relapses in the 24 months after treatment divided by the days on study corresponding to relapse information and multiplied by 365.25.
 
Time on study with relapse information (days) = it is the time on study bounded by 366.25 for patients with relapse information only for the first year; it is the time on study bounded by 731.5 for patients with relapse information in the first year and in the second year.
	
The population estimate will be based on the average of ARR values for the patients in the study. The corresponding 95% CI will be reported. The Statistical Analysis System (SAS)® MEANS procedure will be used to compute these quantities. The following descriptive statistics will be reported: mean, SD, min, max, median, first quartile (Q1), and third quartile (Q3).
	
Patients discontinuing early are analyzed according to number of years of follow-up on treatment and number of relapses observed up to the time of discontinuation.

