Sensitivity (FAS)	
Model-based ARR, defined as expectation of reported relapses divided by time on study with relapse information.
	
The estimate of the expected ARR at Month 24 using the definition considering all the reported relapse data will be based on NB model for relapse count using the total number of reported relapses in the 24 months after treatment, with the offset equal to the log of years on study with relapse information and adjustment for categorical number of relapses in the last 2 years, or since MS diagnosis if diagnosis <24 months (<math>\leq 1</math> relapse, <math>>1</math> relapse).
 
NB regression will be computed with the SAS® GENMOD procedure, using the dist=NB option in the MODEL statement.
	
Patients discontinuing early are analyzed according to the number of years of follow-up on treatment and the number of relapses observed up to the time of discontinuation.

ARR: annualized relapse rate; CI: confidence interval; FAS: Full Analysis Set; GENMOD: generalized linear model; NB: negative binomial; PP: per protocol; SAS: Statistical Analysis System; SD: standard deviation.

\* The sensitivity analysis with the zero-inflated binomial model will be considered only if the number of patients without relapses is greater than 5%. Goodness of fit: Standardized deviance residuals will be plotted against the linear predictor to assess the goodness of fit of the model.

The primary endpoint is derived from the number of relapses collected through the eCRF forms “MS Relapse Report” and “MS Relapse Report Details.” A patient will have 0 relapses (at Visit 3 and/or Visit 6) if they reply “No” to the leading question, “Has patient experienced a new MS relapse since last scheduled or unscheduled visit? (Yes, No).” For patient replies of “Yes,” the

number of relapses will be derived from the records in the “MS Relapse Report Details” form. If at Visit 3, the answer to the leading question is not collected, the number of relapses in the first year and the total number of relapses during the second year will be missing. If at Visit 6, the answer to the leading question is not collected, the number of relapses during the second year will be missing.

For ongoing patients during the study, the time on study will take into account the patient’s last available date. This will be used in the interim analyses for all ARR evaluations (primary objective, sensitivity analyses, and secondary analyses).

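### In the all-reported-relapse sensitivity ARR, exposure for patients with first-year information only is capped at a nominal 366.25 days, not ended at the Visit 3 that ascertained their relapses

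*SAP*

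**What the plan says.** **Exposure.** The all-reported sensitivity ARR in SAP 14.1.1 uses time on study with relapse information. For patients with the first year only, "it is the time on study bounded by 366.25 for patients with relapse information only for the first year"; otherwise "it is the time on study bounded by 731.5 for patients with relapse information in the first year and in the second year". Time on study itself is "Date of study completion or date of study discontinuation - date of first dose of cladribine tablets + 1".

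**Purpose.** SAP 14.1.2 says that the exposure is meant to be limited to the time for which relapse information exists.

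**Numerator.** SAP 14.1.1 counts the "total number of reported relapses in the 24 months after treatment". SAP 14.1.2 describes instead the relapses available for the first year when the second year is missing.

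**Ascertainment.** Under SAP 14.1.1 the count comes from a leading question at Visit 3 and Visit 6. With no Visit 6 answer, the second-year count is missing. Protocol 9.1.1 says: "Post-enrollment relapse count data will be collected at Month 12 (end of Year 1) and Month 24 (end of Year 2) only". Footnote i to Table 1 in Protocol 9.2.4 says instead that the relapse count is kept on a running page and updated throughout follow-up. Protocol 9.2.4 also says that "the timing of study visits is approximate and not mandated by the study protocol".

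**Reuse.** The same definition feeds a negative binomial model (SAP 14.1.1), the subgroups by study completion, treatment completion and MS type and the multiple imputation (SAP 14.1.4), and the hospitalization and glucocorticoid ARRs (SAP 14.2).

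**The concern.** A rate is interpretable only if its numerator and denominator cover the same period. Here the denominator stops at a calendar limit, while the numerator depends on the date on which the site last asked about relapses. For a first-year-only patient that date is Visit 3.

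If Visit 3 comes early and the patient stays on study, the days between Visit 3 and the cap enter as relapse-free although nobody asked about them. If Visit 3 comes late, a relapse between the cap and Visit 3 falls within the 24-month numerator of SAP 14.1.1 but outside the counted time.

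This analysis exists to show whether the ARR is robust to missing second-year data. The rule as written does not fully deliver the aim stated in SAP 14.1.2, and the mismatch carries into every analysis that reuses it.

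**Working it through.** **The plan's own figures.** SAP 9 gives "1 month = 30.4375 days, 1 year = 365.25 days". With the inclusive-day convention (+1):

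- 1 × 365.25 + 1 = 366.25 days
- 2 × 365.25 + 1 = 731.5 days

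Both limits reproduce exactly. They are nominal anniversaries, unrelated to any visit date.

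**Per-patient distortion.** Exposure used = min(time on study, 366.25). Assume a constant relapse rate, relapses counted up to Visit 3, and a patient followed past day 366. Then reported/true = (day of Visit 3) / 366.25. The documents do not give actual Visit 3 days, so the days below are assumptions.

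| Visit 3 day (assumed) | Reported/true |
|---|---|
| 305 | 305/366.25 = 0.833 |
| 335 | 335/366.25 = 0.915 |
| 366.25 | 1.000 |
| 396 | 396/366.25 = 1.081 |
| 456 | 456/366.25 = 1.245 |

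For a drift of about 30 days the error is thus −8.5% to +8.1%.

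**Example with one relapse.** Under the cap, the ARR is 365.25/366.25 = 0.997 whichever day Visit 3 fell on. With exposure ended at Visit 3 it is 365.25/335 = 1.090 or 365.25/396 = 0.922.

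**Two limits on this.**

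- The rule is a cap. A patient who leaves on day 340 contributes 340 days. With Visit 3 on day 335 and exit on day 350, the ratio is 335/350 = 0.957, not 0.915.
- The upward error needs relapses after day 366.25 to be counted. The SAP 14.1.1 numerator allows that. If the SAP 14.1.2 wording governs and relapses are cut at one year by onset date, a late Visit 3 does no harm and only the downward error remains.

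**Effect on the mean ARR.** Let s be the share of first-year-only patients, all with Visit 3 on the same day and with the same true mean rate as the others. Factor = (1 − s) + s × (Visit 3 day)/366.25.

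| s (assumed) | Day 335 | Day 396 |
|---|---|---|
| 10% | 0.9 + 0.1 × 0.915 = 0.9915 | 0.9 + 0.1 × 1.081 = 1.0081 |
| 30% | 0.7 + 0.3 × 0.915 = 0.9744 | 0.7 + 0.3 × 1.081 = 1.0244 |

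That is about 1% at a 10% share and about 2.5% at a 30% share. Drift in both directions would partly cancel.

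**Patients with both years.** Their numerator is limited to 24 months and their exposure to 731.5 days, so the periods broadly agree if study completion coincides with Visit 6.

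**The case against.** The strongest reply is that the cap was introduced to solve this very problem, that the remaining error is small and of either sign, and that it touches sensitivity analyses only. All of that is right. It limits the size of the point but does not remove it, since the stated aim is time with relapse information and the rule uses an anniversary.

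A second reply is that relapses may be collected continuously, as the footnote to Table 1 says, so that Visit 3 is not the end of ascertainment. That may be so. But Protocol 9.1.1 says the opposite, and SAP 14.1.1 still treats the second year as missing without a Visit 6 answer. The documents have to settle it.

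A reader might also infer that interim ARRs are diluted, because SAP 14.1.1 says "For ongoing patients during the study, the time on study will take into account" the last available date. The documents do not support that:

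- The first two interim analyses include no relapse endpoint, and the third is on 12-month data.
- The 12-month ARR in SAP 14.2 has a one-year maximum, and the all-reported ARR for first-year-only patients is capped.
- For the uncapped 24-month ARR, SAP 14.1.1 and 14.1.4 make a patient's value missing when the Visit 6 answer is absent; they do not divide a first-year count by longer time.
- The SAP version is dated 23 January 2025, after the planned last visit of 3 January 2025. The rule for ongoing patients is therefore probably moot (an inference, as interim dates are not given).

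Nor does the point reach the primary ARR. No fault is shown in its exposure definition. Moving it to the last assessment could discard relapses observed up to discontinuation, which the primary analysis is meant to use.

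**Conclusion.** The point holds for the all-reported-relapse definition and its reuses. For first-year-only patients, the exposure limit and the end of relapse ascertainment are different dates, and the numerator is described in two ways. A drift of about 30 days distorts an affected patient's rate by about −8.5% to +8.1%, and the mean ARR by about 1% to 2.5% at assumed shares of 10% to 30%.

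These sizes rest on a constant relapse rate, follow-up past day 366, relapses counted to Visit 3, and drift in one direction. Neither the share of such patients nor their Visit 3 dates are in the documents. The consequence is modest, but the correction is cheap and makes the rule do what SAP 14.1.2 says it should.

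**What to change.** For the all-reported definition only, and wherever it is reused in SAP 14.1.1, 14.1.4 and 14.2:

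1. End exposure at the earlier of study exit and the date of the last completed relapse assessment. That is Visit 3 or Visit 6, or the last running-page review if collection is continuous.
2. Count only relapses with onset from first dose to that date and within 24 months. Protocol 9.3 already collects onset dates.
3. Give the numerator the same wording in SAP 14.1.1 and 14.1.2.
4. Reconcile Protocol 9.1.1 with footnote i to Table 1 on how relapses are collected, and state in the SAP which governs.

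Leave the primary ARR definition unchanged.

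The cost is one derived date and no new data. Some patients contribute slightly less person-time, and relapses with onset after the last assessment leave this sensitivity count.

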- Relapse of MS during the study period as determined by the investigator (see Section 9.1.2.1 for a guide on definition) including date of onset, resolution of relapse and definition for relapse used
- Relapse of MS associated with hospitalization (relapse as primary diagnosis or reason for hospitalization) during the study period as determined by the investigator (see Section 9.1.2.1 for a guide on definition) including date of onset, resolution of relapse and definition for relapse used
- Relapse of MS associated with glucocorticoid use during the study period as determined by the investigator (see Section 9.1.2.1 for a guide on definition) including date of onset, resolution of relapse and definition for relapse used
- MRI scans from all MRIs performed during the study period; MRI scans are assessed by a central neuroradiology center; data includes: CCI [REDACTED]
[REDACTED]
[REDACTED]
[REDACTED]
- Results of neurological examination as per standard of care (Kurtzke FSS, ambulation up to 5000 meters and EDSS)
- Hematology assessment (white blood cell count, hemoglobin, hematocrit, platelet count, ALC). If the investigator assesses CCI [REDACTED] or immunoglobulin levels, these data should be recorded as well
- Pregnancy, HIV, hepatitis B, hepatitis C and tuberculosis test results
- Comorbid conditions
[REDACTED]
[REDACTED]
- AEs as a continuous log
- ePRO assessments (treatment adherence questions based on modified versions of the MS-TAQ, TSQM, SF-36, MFIS-5, BDI-FS, WPAI-MS, PDDS)

Derived and transformed data needed for the analysis are described in Section 9.7.2.

[figure not shown]

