#### **14.1.2 Sensitivity Analyses of the ARR**

For the NB model, the least squares means estimates of the ARR at Month 24 and the associated CI will be reported for patients having, respectively,  $\leq 1$  relapse or  $>1$  relapse in the previous 2 years, or since MS diagnosis, if diagnosis is  $<24$  months. These quantities will be obtained using the LSMEANS statement with the ILINK option.

For the zero-inflated NB model, the following approach will be used to report the estimates of the ARR at Month 24 and associated CIs for patients having, respectively,  $\leq 1$  relapse or  $>1$  relapse in the previous 2 years, or since MS diagnosis, if diagnosis is  $<24$  months. The STORE statement in PROC GENMOD will be used to save the fitted model. Then the fitted model will be used in proc PLM with the SCORE statement and the ILINK and NOOFFSET options.

Standardized deviance residuals will be plotted against the linear predictor to assess the goodness of fit of the model (NB or zero-inflated NB). The STDRESDEV statement with the XBETA option in the GENMOD procedure will be used.

A further sensitivity analysis will be carried out considering different definitions of the ARR based on all reported relapses. Such additional definitions will derive the ARR over the 24 months using the number of available relapses over the first year even if information on the relapses in the second year is missing. The time on study for the calculation of the ARR will be bounded by the time on study with relapse information. Such logic will be used also for an additional sensitivity analysis using the NB model.

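### A No at Visit 3 or Visit 6 is scored as zero relapses, but the question covers only the time since the last visit, so earlier relapses that year can drop out of the primary ARR

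*SAP*

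**What the plan says.** SAP 14.1.1 derives the primary endpoint from two eCRF forms, the MS Relapse Report and its Details form. The leading question is "Has patient experienced a new MS relapse since last scheduled or unscheduled visit". The scoring rule begins "A patient will have 0 relapses (at Visit 3 and/or Visit 6) if they reply" No. For a Yes, the "number of relapses will be derived from the records in the" Details form.

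The missing-answer rule follows. If the Visit 3 answer is not collected, "the number of relapses in the first year and the total number of relapses during the second year will be missing". If the Visit 6 answer is not collected, the second-year count is missing. Each patient's ARR is the number of relapses "divided by the number of days on study for that patient and multiplied by 365.25".

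The protocol gives two accounts of when relapses are recorded. Section 9.1.1 restricts collection of post-enrollment relapse counts to Months 12 and 24, and the relapse-count row of Table 1 marks only those visits. Footnote i to Table 1 says relapse counts go on a running page as information arises. Section 9.3 lists "Relapse of MS during the study period as determined by the investigator", with onset and resolution dates, among the variables to be collected.

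One set of sensitivity analyses uses the "total number of reported relapses in the 24 months after treatment". SAP 14.1.2 describes these as "using the number of available relapses over the first year even if information on the relapses in the second year is missing".

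**The concern.** The question's recall period and the period it is used to score do not match. The missing-answer rule treats the Visit 3 answer as first-year status and the Visit 6 answer as second-year status, but the question reaches back only to the most recent visit of any kind. A relapse before that visit can be followed by a truthful No and scored as zero. An unscheduled visit shortens the look-back further, so a relapse that itself prompted such a visit falls outside the question unless it was recorded at that visit and that record is counted.

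The denominator remains all days on study, so the error runs one way: the ARR can fall but cannot rise. If the same counts are reused, the negative binomial models, the 12-month ARR, the relapse proportions and the hospitalisation and glucocorticoid ARRs are affected as well. The retrospective ARR in SAP 11.3 counts all relapses in its window without this rule, so the two reported rates could rest on different bases.

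**Working it through.** **No figure to reproduce.** The readable text gives no expected ARR or dispersion, so those values below are assumptions.

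**Look-back on schedule.** Protocol 9.1.1 expects visits at Months 2, 6, 12, 14, 18 and 24. The visit before Visit 3 is at Month 6 and the visit before Visit 6 is at Month 18. The two questions therefore cover (12 − 6) + (24 − 18) = 12 of 24 months. With unscheduled visits at, say, Months 9 and 21 (assumed), they cover 3 + 3 = 6 of 24 months.

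**One patient.** Take one relapse at Month 4, No at Visits 3 and 6, and 731 days on study. The ARR should be 1/731 × 365.25 = 0.50. The rule as written gives 0.

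**Expected loss.** Let L be the months since the last visit, f = L/12, λ the true ARR and k the negative binomial dispersion. Assume a constant rate within patient, the same L for everyone and full 24-month follow-up.

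- Case A, only relapses inside the look-back count: share lost = 1 − f, whatever λ and k.
- Case B, a Yes brings in all of that year's records and a No gives zero: share lost = (1 − f) × (1 + kλf)^−(1/k + 1).
- Patients with any counted relapse in 24 months, either case, at k = 1: 1 − 1/(1 + 2λf).

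For example, in case B with L = 6, λ = 0.15 and k = 1, the share lost is 0.5 × 1.075^−2 = 0.43, so the derived ARR is 0.15 × 0.57 = 0.085.

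At λ = 0.15 and k = 1:

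| L (months) | Loss, A | ARR, A | Loss, B | ARR, B | Any relapse |
|---|---|---|---|---|---|
| 12 | 0% | 0.150 | 0% | 0.150 | 23.1% |
| 10 | 17% | 0.125 | 13% | 0.130 | 20.0% |
| 6 | 50% | 0.075 | 43% | 0.085 | 13.0% |
| 3 | 75% | 0.038 | 70% | 0.045 | 7.0% |

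**Range for case B** over λ = 0.10–0.30 and k = 0.5–2: 9–15% at L = 10, 34–46% at L = 6 and 61–72% at L = 3. The six-month extremes are 0.5 × 1.025^−3 = 46% (λ = 0.10, k = 0.5) and 0.5 × 1.3^−1.5 = 34% (λ = 0.30, k = 2). Gamma-Poisson simulation gives the same ranges.

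**Does a planned analysis remove the problem?** The all-reported-relapses analyses allow first-year relapses to be used when the second year is missing. Nothing says that a record is restored when the Visit 3 or Visit 6 answer is No.

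**The case against.** The best defence is that the form is completed interval by interval. The SAP ties the zero to the visit at which it is given, never says that dated records are discarded, and does not state that details are read *only* after a Yes. The question's wording suits a form filled in repeatedly, and the running page, the relapse module mentioned in Protocol 11.1 and the dated relapse variable in Protocol 9.3 all fit that. The entries together would then cover all follow-up.

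This reading conflicts with two statements. Protocol 9.1.1 limits collection of relapse counts to Months 12 and 24. And if the Visit 3 answer covered only one interval among several, its absence would not make the whole first-year count missing, as the SAP says it does.

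The alternative defence is that the form exists only at Months 12 and 24 and sites naturally answered for the year. That may be so, but it departs from the question as worded. The eCRF is not in the documents, so neither defence can be confirmed.

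It can also be said that counting all reported relapses, read plainly, includes every record. That is possible but not stated, and it would protect only sensitivity analyses, not the primary one.

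What stands is that the loss may be nil, that every non-zero figure depends on the literal reading and assumed inputs, and that bias has not been shown to have occurred.

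**Conclusion.** The concern holds. The stated derivation of the primary endpoint can return a wrong count, and any error lowers the ARR. The actual size cannot be known from the documents. It is nil if sites answered for the whole year or if all dated records are counted. Under the literal reading with visits on schedule, it is 50% in case A and 34–46% in case B. These figures illustrate the mechanism and are not bounds. They rest on a constant relapse rate, a common six-month look-back and, for case B, an assumed ARR of 0.10–0.30 and dispersion of 0.5–2. Because this is the primary derivation, the rule must be corrected rather than left for programmers to interpret.

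**What to change.** 1. In SAP 14.1.1, derive the primary count and every other relapse count from all dated relapse records with onset from first dose to the end of the period, whatever the Visit 3 or Visit 6 answer. Let a No stand for zero only over the interval the question covers.
2. Before database lock, query patients with a No at Visit 3 or Visit 6 whose earlier months of that year are not confirmed relapse-free. Report how many remain unconfirmed.
3. In SAP 14.1.2, state whether the all-reported-relapses analyses include records from patients who answered No.
4. Reconcile the Months 12 and 24 restriction in Protocol 9.1.1 with footnote i to Table 1.

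The cost is one derivation change, some SAP and protocol wording and one round of site queries. Protocol 9.3 already calls for onset dates. Time for queries is short: SAP version 4.0 is dated 23 January 2025 and lock was planned for 17 February 2025, 25 days later, although SAP 6.5 expects the cutoff by the end of March 2025. If all dated records are already counted, step 1 needs only a clarifying sentence. Otherwise the reported ARR may rise.
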